## **7.0 Demographics, Baseline Characteristics, Medical History, and Previous/Concomitant Medications**

### **7.1 Demographic and Baseline Characteristics**

Demographics and baseline characteristics will be summarized for the Safety Population.

Demographics include age, weight, and body mass index (BMI) as continuous variables, and gender, race ethnicity, age category (< 50 years and ≥ 50 years; < 65 years and ≥ 65 years), birth year (< 1945, 1945 to 1965, > 1965), BMI category (< 30 kg/m^2 and ≥ 30 kg/m^2), and geographic region (North America, Europe, Australia/New Zealand, Latin America ), original study as categorical variables. Baseline characteristics will include HCV genotype/subtype (1a, 1b, other 1 subtype), IL 28B genotype (CC, CT, and TT; CC and non-CC), initial DAA combination study prior to Study M13-101, treatment

status at entry to initial DAA combination study prior to Study M13-101 (treatment naïve or treatment experienced [null responder, partial responder or relapser]), type of response to HCV treatment in initial DAA combination study (null responder, partial responder, relapser), treatment in the initial DAA combination study, baseline  $\log_{10}$  HCV RNA levels (continuous), history of diabetes, baseline fibrosis score (F0 – F1, F2, F3, F4), baseline HCV RNA levels ( $< 800,000$  IU/mL or  $\geq 800,000$  IU/mL), baseline IP-10 ( $< 600$  ng/L or  $\geq 600$  ng/L) and baseline HOMA-IR (fasting glucose [MMOL/L]  $\times$  fasting insulin [MCIU/ML]/22.5,  $< 3$  mU  $\times$  mmol/L or  $\geq 3$  mU  $\times$  mmol/L). Subjects who do not have a fasting glucose and fasting insulin value at Baseline will be excluded from the summary of baseline HOMA-IR.

Summary statistics (N, mean, median, SD, and range) will be generated for continuous variables (e.g., age and BMI). The number and percentage of subjects will be presented for categorical variables (e.g., gender and race). Summary statistics for baseline weight will be computed overall and separately by gender.

IL28B rs12979860 genotype was resulted as C/C, C/T, T/T, or Unable to Assign Genotype by the central laboratory or Abbott/AbbVie Pharmacogenetics group in the initial DAA combination study.

History of diabetes is defined as presence of "Metabolic/Diabetes mellitus" on the MH eCRF.

Baseline fibrosis stage is defined for subjects with non-missing liver biopsy scores, FibroScan scores, or FibroTest scores in the initial DAA combination study. In general, subjects will be categorized as F0 – F1, F2, F3, or F4 according to the Metavir mapping defined in Table 4. If a subject has more than one score recorded, then only one score will be used to categorize the subject. If a biopsy score is present, then it will be used to categorize the subject, regardless of the FibroScan/FibroTest score. Similarly, if a FibroScan score is present along with a FibroTest score, then the FibroScan score will be used to categorize the subject. If biopsy and FibroScan scores are not present and more than one FibroTest result is available, then the Baseline FibroTest result (i.e., last

non-missing FibroTest result on or before Day 1 of the initial DAA combination study) will be used to categorize the subject. In some studies, the investigator used the mapping and put the result in the eCRF and this result is used directly per the initial DAA combination study SAP.

**Table 4. Baseline Fibrosis Stage**

Baseline Fibrosis Stage, Metavir Equivalents	Liver Biopsy Metavir, Batts Ludwig, Knodell, IASL, Scheuer, New Inuyama or Laennec Score	Liver Biopsy Ishak Score	FibroScan (kPa)	FibroTest
F0 – F1	0 or 1	0, 1, or 2	< 8.8	≤ 0.48
F2	2	3	≥ 8.8 to < 9.6	0.49 to 0.58
F3	3	4	≥ 9.6 to < 14.6	≥ 0.59 to 0.72
F4	4	≥ 5	≥ 14.6	≥ 0.73

## 7.2 Medical History

Medical history data will be summarized overall for the Safety Population. Medical history data will be summarized and presented using body systems and conditions/diagnoses as captured on the eCRF. The body systems will be presented in alphabetical order and the conditions/diagnoses will be presented in alphabetical order within each body system. The number and percentage of subjects with a particular condition/diagnosis will be summarized. Subjects reporting more than one condition/diagnosis within a body system will be counted only once for that body system.

The subject's medical history will be transferred from the initial Abbott/AbbVie DAA combination study to the Study M13-101 EDC system. The subject's medical history will then be updated at the Screening Visit with any relevant information that was not collected in the initial Abbott/AbbVie DAA combination study and any new medical history that occurred between the end of the initial Abbott/AbbVie DAA combination study and this study. The subject's medical history will also be updated if needed for the

period between the Screening Visit and the TI Day 1 Visit. The updated medical history as of TI Day 1 will serve as the baseline for clinical assessment.

### **7.3 Previous HCV Treatment and Concomitant Medications**

Prior HCV medications, concomitant medications and post-DAA treatment HCV medications will be summarized for the Safety Population. A prior HCV medication is defined as pegIFN/RBV after terminating the initial Abbott/AbbVie DAA combination study and prior to enrolling in Study M13-101 and also the study drug regimen taken in the initial Abbott/AbbVie combination DAA trial. A concomitant medication is defined as any medication that started prior to the first dose of study drug and continued to be taken after the first dose of study drug or any medication that started after the first dose of study drug, but not after the last dose of DAA study drug. Medications related to HCV antiviral therapy and medications prescribed in association with treatment due to an SAE will be collected during Substudy 2 and Substudy 3. Post-DAA treatment medications related to HCV antiviral therapy will be summarized and are defined as any medications started on or after the last dose of DAA study drug and entered as a post-treatment HCV medication on the eCRF.

The number and percentage of subjects taking concomitant medications and post-treatment HCV medications will be summarized based on the WHO Drug Dictionary.

### **8.0 Patient Disposition**

The number of subjects for each of the following categories will be summarized overall and by investigator:

- Enrolled subjects
- Subjects who took at least one dose of DAA study drug in Substudy 1
- Subjects who discontinued DAA treatment in Substudy 1
- Subjects who completed DAA treatment
- Subjects who continued into Substudy 2

- Subjects who discontinued pegIFN/RBV (i.e., subjects who did not enter Substudy 2 or subjects who entered Substudy 2 and prematurely discontinued pegIFN/RBV during Substudy 2)
- Subjects who completed the study
- Subjects who discontinued from the study

The number and percentage of subjects who discontinued study drug in Substudies 1 and 2 will be summarized by reason (all reasons) and by primary reason (collected on eCRF). The number and percentage of subjects who discontinued from the study will be summarized by reason (all reasons) and by primary reason as recorded on the eCRF.

The number and percentage of subjects RBV dose modification will be summarized. Reasons for study drug interruptions and RBV dose modifications will be presented in the listings.

## **9.0 Study Drug Exposure and Compliance**

The duration of exposure to DAA therapy will be summarized overall for the Safety Population. Duration of exposure is defined for each subject as the last DAA dose date minus the first DAA dose date plus 1 day (i.e., any study drug interruptions will not be subtracted out). Descriptive statistics (mean, standard deviation, median, minimum, and maximum) will be presented. The duration of DAA therapy will also be summarized with frequencies and percentages using the following categories: 1 to 30 days, 31 to 60 days, 61 to 90 days, 91 to 120 days, 121 to 150, and  $\geq 151$  days.

Similarly, the duration of exposure to pegIFN and RBV across Substudies 1 and 2 will be summarized. Duration of exposure to pegIFN therapy across Substudies 1 and 2 is defined for each subject as the last pegIFN injection date minus first pegIFN injection date plus 7 days and will be summarized and analyzed similarly to DAA. Duration of exposure to RBV therapy across Substudies 1 and 2 is defined for each subject as the last RBV dose date minus first RBV dose date plus 1 day and will be summarized and analyzed similarly to DAA. The following categories will be used for pegIFN and RBV:

1 to 30 days, 31 to 60 days, 61 to 90 days, 91 to 120 days, 121 to 150 days, 151 to 180 days, 181 to 210 days, 211 to 240 days, 241 to 270 days, 271 to 300 days, 301 to 330 and  $\geq 331$  days.

The compliance to each DAA study drug (ABT-450, ABT-267) and ritonavir during the first 24 weeks of treatment (Substudy 1) will be calculated as the percentage of capsules/tablets taken over the total capsules/tablets prescribed. The total number of capsules/tablets prescribed will be equal to the total number of capsules/tablets that should have been taken per the protocol for the duration that the subject was in the TI Period (Substudy 1). Study drug interruptions captured on the eCRF will be subtracted when calculating compliance. Compliance will be summarized with the mean, median, standard deviation, minimum and maximum percentage for each DAA and ritonavir. A subject is considered to be compliant if the percentage is between 80% and 120% during the first 24 weeks of treatment (Substudy 1). The percentage of subjects who are compliant to each study drug will be summarized. A subject listing of compliance will be provided also.

## **10.0 Efficacy Analysis**

### **10.1 General Considerations**

#### **General Considerations**

All efficacy analyses will be performed for the ITT population, unless otherwise specified. Analyses of primary and secondary endpoints will be performed for the overall treatment cohort. No statistical comparisons will be made. Analyses of additional endpoints will be performed for the overall treatment cohort. A 95% confidence interval based on Wilson score test will be provided.

Plasma HCV RNA levels will be determined for each sample collected by the central laboratory using the Roche COBAS TaqMan® real-time reverse transcriptase-PCR (RT-PCR) assay V2.0. For this assay, the LLOD is 15 IU/mL and the LLOQ is 25 IU/mL. HCV RNA results that are detectable but not quantifiable are reported as

"< 25 IU/mL HCV RNA detected" and those that are undetectable are reported as "HCV RNA not detected" in the database.

The notation "HCV RNA < LLOQ" is used to represent all HCV RNA values < 25 IU/mL, including values reported as "HCV RNA NOT DETECTED" or "< 25 IU/mL HCV RNA DETECTED." HCV RNA  $\geq$  LLOQ are all quantifiable values of 25 IU/mL or greater.

If a subject discontinues the study drug and subsequently starts another HCV treatment, this subject's HCV RNA values after the time he/she starts another HCV treatment will be excluded from analyses.

All HCV RNA endpoints will be defined using the LLOQ. Imputations for missing values will be performed for analyses of RVR, Final Treatment Visit response, eRVR, SVR4, SVR12, SVR24 as specified in Section 6.0.

### **Definitions for Efficacy Endpoints**

Note that a confirmed quantifiable post-treatment value is defined as any two consecutive post-treatment HCV RNA measurements  $\geq$  LLOQ. During treatment, a confirmed quantifiable value is defined as any two consecutive HCV RNA values  $\geq$  LLOQ, either both during treatment or at the final treatment measurement and the next consecutive post-treatment measurement.

**RVR** (Rapid Virologic Response) = HCV RNA < LLOQ at TI Week 4.

**eRVR** (extended rapid virologic response) = HCV RNA < LLOQ at TI Weeks 4 through 12 without a confirmed HCV RNA  $\geq$  LLOQ between TI Weeks 4 and 12.

**Final Treatment Visit Response** = HCV RNA < LLOQ at the end of treatment (i.e., at completion of all study drugs: DAAs, pegIFN, and RBV); this corresponds to the Final Treatment Visit value (see Section 6.0).

**Breakthrough** = confirmed increase from nadir in HCV RNA (two consecutive HCV RNA measurements  $> 1 \log_{10}$  IU/mL above nadir) at any time point during treatment or confirmed HCV RNA  $\geq$  LLOQ after HCV RNA  $<$  LLOQ during treatment. A single breakthrough value ( $\geq$  LLOQ or  $> 1 \log_{10}$  above nadir) followed by lost to follow-up would be considered a breakthrough (i.e., will not require confirmation).

**On-treatment virologic failure = breakthrough** or failure to suppress during treatment (all on-treatment values of HCV RNA  $\geq$  LLOQ ) with at least 6 weeks (defined as active study drug duration  $\geq 36$  days) of treatment.

**SVR24** (referred to as SVR24actual in the protocol) = HCV RNA  $<$  LLOQ in the SVR24 window (24 weeks after the last actual dose of study drug [including DAA, pegIFN, and RBV]) without any confirmed quantifiable ( $\geq$  LLOQ) post-treatment value before or during that SVR window.

**SVR12** (referred to as SVR12actual in the protocol) = HCV RNA  $<$  LLOQ in the SVR12 window (12 weeks after the last actual dose of study drug [including DAA, pegIFN, and RBV]) without any confirmed quantifiable ( $\geq$  LLOQ) post-treatment value before or during that SVR window.

**SVR4** = HCV RNA  $<$  LLOQ in the SVR4 window (4 weeks after the last actual dose of active study drug) without any confirmed quantifiable ( $\geq$  LLOQ) post-treatment value before or during that SVR window.

**Relapse12** = confirmed HCV RNA  $\geq$  LLOQ between Final Treatment Visit and 12 weeks after last actual dose of study drug (up to and including SVR12 assessment time point) for a subject with HCV RNA  $<$  LLOQ at the Final Treatment Visit who completes treatment. Completion of treatment is defined as DAA duration  $\geq 161$  days and pegIFN/RBV duration  $\geq 252$  days.

**Relapse24** = confirmed HCV RNA  $\geq$  LLOQ within the SVR24 window for a subject who achieved SVR12 and has HCV RNA data available in the SVR24 window.

**Relapseoverall** = confirmed HCV RNA  $\geq$  LLOQ between Final Treatment Visit and up to and including the last HCV RNA measurement collected in the PT Period for a subject with HCV RNA  $<$  LLOQ at Final Treatment Visit who completes treatment. Completion of treatment is defined as DAA duration  $\geq$  161 days and pegIFN/RBV duration  $\geq$  252 days.

**Relapselate** = confirmed HCV RNA  $\geq$  LLOQ at any time after the SVR24 assessment time point for a subject who achieved SVR24 and has post-SVR24 HCV RNA data available.

If the last available post-treatment value is  $\geq$  LLOQ, then the subject will be considered a relapse (i.e., will not require confirmation). Relapse analyses will exclude subjects who do not have any post-treatment HCV RNA values.

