5.4 Removal of Subjects from Therapy or Assessment

5.4.1 Discontinuation of Individual Subjects

Each subject has the right to withdraw from the study at any time. In addition, the investigator may discontinue a subject from the study at any time if the investigator considers it necessary for any reason, including the occurrence of an adverse event or noncompliance with the protocol.

If, during the course of study drug administration, the subject prematurely discontinues during the Substudy 1 Treatment Intensification Period, the procedures outlined for the Treatment Intensification Discontinuation (TI D/C) Visit should be completed as defined in [Table 5](#). Ideally, this should occur no later than 2 days after their final dose of study drug, and prior to the initiation of any other anti-HCV therapy. However, these procedures should not interfere with the initiation of any new treatments or therapeutic modalities that the investigator feels are necessary to treat the subject's condition. The dosing end dates for each DAA and ritonavir and reason for discontinuation from Substudy 1 will be recorded in the eCRF.

The subject should continue to Substudy 2, the pegIFN/RBV Treatment Period, unless the investigator considers continued pegIFN and RBV inappropriate due to either intolerance or inadequate virologic response. If the subject prematurely discontinues during Substudy 2, the subject should return for PR D/C visit procedures as defined in [Table 5](#) and proceed to Substudy 3. If the investigator does not consider the subject appropriate to participate in Substudy 2, the subject should start Substudy 3, the Post-treatment Period for monitoring of HCV resistance and viral response. Following discontinuation of study drug, the subject will be treated in accordance with the investigator's best clinical judgment. The dosing end dates for RBV and pegIFN and reason for discontinuation from Substudy 2 will be recorded in the eCRF.

If a subject discontinues from the Post-treatment Period, the subject should return for post-treatment discontinuation procedures (PT D/C) as defined in [Table 7](#). The reason for discontinuation from Substudy 3 will be recorded in the Study Completion eCRF.

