**Table 3. Post-Treatment (Substudy 3) Visit Windows**

Scheduled Time	Nominal (Study Drug End Day)	Time Window (Study Drug End Days Range)
PT Week 2	14	3 to 21
PT Week 4	28	22 to 42
PT Week 8	56	43 to 70
PT Week 12	84	71 to 126
PT Week 24	168	127 to 210
PT Week 36	252	211 to 294
PT Week 48	336	295 to 378
Final Post-Treatment Visit	Study drug end day > 2	
SVR 4	28	3 to 56
SVR 12	84	57 to 126
SVR 24	168	127 to 210

Notes: The result closest to the scheduled timepoint will be used, except for SVR endpoints. For SVR windows, the last value in the window will be used.

Blood samples for chemistry, hematology, and urinalysis are only scheduled to be collected at PT Weeks 2 and 4 during the Post-Treatment Period.

HCV RNA measurements taken after the start of another anti-viral treatment will be excluded.

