#### HCV RNA

HCV RNA values will be selected for analysis based on the analysis windows defined in Section 6.2. When there is no HCV RNA value in a defined visit window, the closest values before and after the window will be used for flanking imputation, regardless of the value chosen for the subsequent and preceding window.

For flanking imputation, if a subject has a missing HCV RNA value at a post-baseline visit but with undetectable or unquantifiable HCV RNA levels at both the preceding value and the succeeding value, then the HCV RNA level will be imputed as undetectable or

unquantifiable, respectively, at this visit for this subject. In addition, if a subject has an unquantifiable HCV RNA level at the preceding value and an undetectable HCV RNA level at the succeeding value, or vice versa, the HCV RNA level will be imputed as unquantifiable at this visit for this subject.

For analyses of SVR, subjects still missing visit values after flanking imputation will have backward imputation applied. For backward imputation, if the nearest HCV RNA value after the SVR window is unquantifiable or undetectable, then it will be used to impute the HCV RNA value in the SVR window.

For analyses of RVR, Final Treatment Visit Response, eRVR, and SVR, subjects still missing a value for the visit window associated with the analysis after performing the imputations described above will be imputed as a failure.

If a subject starts another treatment for HCV, then all HCV RNA values for this subject measured on or after the start date of the new HCV treatment will be excluded from analyses. The subject will be considered a failure for summaries of viral response at all time points after the start of the new HCV treatment.

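### A breakthrough seen once, in a suppressed subject who starts new HCV treatment before a second usable sample, is not counted as on-treatment virologic failure

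*SAP*

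**What the plan says.** **Breakthrough (SAP 10.1, Definitions for Efficacy Endpoints).** Either of two patterns counts: two consecutive values more than 1 log10 above nadir, or a confirmed value at or above LLOQ after an earlier value below it. Confirmation at the LLOQ may come from two consecutive values "either both during treatment or at the final treatment measurement and the next consecutive post-treatment measurement". The only waiver is for a single value "followed by lost to follow-up would be considered a breakthrough (i.e., will not require confirmation".

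**On-treatment virologic failure (same section).** This is breakthrough "or failure to suppress during treatment", where failure to suppress means that all on-treatment values are at or above LLOQ with at least 36 days of drug.

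**Cut-off at a new HCV treatment.** Three places state it:
- SAP 6.3: values "measured on or after the start date of the new HCV treatment will be excluded from analyses".
- SAP 10.1, General Considerations: "this subject's HCV RNA values after the time he/she starts another HCV treatment will be excluded from analyses".
- SAP Table 3 note: "HCV RNA measurements taken after the start of another anti-viral treatment will be excluded".

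SAP 6.3 adds that the subject is a failure in viral response summaries from then on.

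**Relapse (SAP 10.1).** If the last available post-treatment value is at or above LLOQ, "then the subject will be considered a relapse (i.e., will not require confirmation". The reason why no later value exists does not matter.

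**Protocol 5.4.1.1.** HCV RNA of 25 IU/mL or more at TI Week 24 is virologic failure and stops all study drugs. Prompt confirmatory testing is asked for only under the last two criteria on the list (rise from nadir, and breakthrough or relapse).

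**Protocol 5.4.1.** The TI discontinuation visit should ideally take place within 2 days of the final dose and "prior to the initiation of any other anti-HCV therapy", but should not delay treatment that the investigator thinks necessary.

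**The concern.** The SAP has two ways to lose the second value and waives confirmation for only one of them. A subject who drops out after one breakthrough value is counted as a failure. A subject with the same value who stays in follow-up but starts new HCV treatment is not, because SAP 6.3 removes the value that could have confirmed it. Starting a new treatment is a natural response to losing virologic control, so the omission falls on subjects whose regimen probably failed.

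The outputs at stake are the on-treatment virologic failure rate with its Wilson interval, the breakthrough counts by visit, and the SVR12 and SVR24 non-response reasons. The mITT-GT-VF sensitivity analysis may also be affected. SAP 5.1 removes from it those who missed SVR12 for reasons other than virologic failure.

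**Working it through.** **1. One subject through the rules.** Take a subject below LLOQ up to TI Week 20 with at least 25 IU/mL at TI Week 24. All study drugs stop, and new HCV treatment starts before the next sample or on the same date as it.

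- *Two consecutive values?* No. SAP 6.3 discards the second.
- *Lost to follow-up?* Not on an ordinary reading. Protocol 5.1.4 follows everyone with at least one DAA dose for 48 weeks after the last dose.
- *Failure to suppress?* No. Earlier values were below LLOQ.
- *Relapse?* No. It requires a Final Treatment Visit value below LLOQ.
- *Completed treatment?* No. SAP 10.1 requires DAA for at least 161 days and pegIFN/RBV for at least 252. DAA for 24 × 7 = 168 days meets the first; pegIFN/RBV stopped at about the same time does not meet the second.
- *Result.* SVR12 non-responder under reason 3, and SVR24 non-responder under reason 4: early discontinuation with no on-treatment virologic failure.
- *Resistance analyses.* SAP 10.6 takes virologic failure from Section 5.4.1.1, which is in the protocol. There the single TI Week 24 value is enough, so the same subject is a virologic failure in one part of the report and not in another.

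**2. How far the gap extends.** Five constructed subjects were put through the SAP definition. A to D were below LLOQ on days 28, 56 and 84 and quantifiable on day 112.

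| Subject | What follows | On-treatment virologic failure under the SAP? |
|---|---|---|
| A | Lost to follow-up | Yes |
| B | New treatment day 113, next sample day 126 | **No** |
| C | Second quantifiable value day 119, new treatment day 120 | Yes |
| D | Quantifiable post-treatment value day 126, new treatment day 130 | Yes |
| E | Never below LLOQ, one rise above 1 log10 on day 84, new treatment day 85 | Yes (failure to suppress, 84 ≥ 36 days) |

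Only B is misclassified.

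**3. Size.** The SAP gives no figure to reproduce and has no predetermined sample size. N = 35 is the upper figure in the protocol synopsis, used as an assumption. The SAP's Wilson 95% interval is

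(p + z²/2n ± z·√[p(1−p)/n + z²/4n²]) / (1 + z²/n), with z = 1.96.

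One affected subject is 1/35 = 2.9 points of the failure rate. If that subject were the only on-treatment failure, the result moves from 1/35 = 2.9% (0.5 to 14.5%) to 0/35 = 0% (0 to 9.9%).

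For mITT-GT-VF, assume that every non-responder is in truth a virologic failure and that k of them fall into the gap. SVR12 is then s/(35 − k) instead of s/35.

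| Assumed responders s | k = 0 | k = 1 | k = 2 | k = 3 |
|---|---|---|---|---|
| 21 | 60.0% | 61.8% | 63.6% | 65.6% |
| 25 | 71.4% | 73.5% | 75.8% | 78.1% |
| 30 | 85.7% | 88.2% | 90.9% | 93.8% |

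The rise is 1.8 to 2.5 points for k = 1 and 5.6 to 8.0 points for k = 3. ITT SVR12 stays at the k = 0 value throughout.

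**The case against.** A reader might infer that any subject who breaks through and is switched is reported as having no virologic failure. The documents do not support that: subjects C, D and E are all counted. Nor does a single quantifiable value in mid-treatment, say at TI Week 16, normally lead to a stop. The protocol criterion that applies there needs two consecutive values and prompt confirmation, so a subject stopped under it already meets the SAP definition. An investigator may still stop a subject for other reasons, but that is an uncommon path.

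A reader might also infer bias in the primary endpoint. There is none, because SAP 6.3 makes the subject a non-responder whatever the stated reason.

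Three further points have weight:
- Lost to follow-up is not defined in the SAP. A programmer could take it to mean that no later usable value exists, which would close the gap. That is a reason to write it down, since the result should not depend on who reads it.
- SAP 5.1 does not tie virologic failure to the reason list in SAP 10.1, so the mITT-GT-VF effect depends on that reading.
- Non-responders are listed and post-DAA HCV medications are summarised, so an affected subject could be traced. The summary rates would still be wrong.

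At TI Week 24, a discontinuation-visit or PT Week 2 sample taken before the switch would supply confirmation. The protocol makes that timing an aim rather than a requirement. A sample on the start date itself is discarded under SAP 6.3 but arguably kept under SAP 10.1 and the Table 3 note.

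**Conclusion.** The point holds in a narrow form. It needs three things together: earlier suppression on treatment, one unconfirmed breakthrough value, and new HCV treatment before a second usable sample. The clearest route is the TI Week 24 criterion, where the protocol acts on one value and the SAP's efficacy and resistance sections then classify the same subject differently.

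The error runs one way: on-treatment failure is understated and, if SAP 5.1 is read through the reason list, the sensitivity SVR12 is overstated. Each subject is worth 2.9 points of the failure rate at N = 35, and one subject adds 1.8 to 2.5 points to mITT-GT-VF SVR12 over the assumed range of 21 to 30 responders. Sample size, responder counts and number affected are all assumptions. The documents do not show that any subject is affected. The change is still worth making before analysis, because the stated rule gives the wrong label when the case arises and the SAP already contains the remedy.

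**What to change.** 1. In SAP 10.1, state that a single breakthrough value that is the last HCV RNA value available for analysis, including because another HCV treatment was started, counts as breakthrough without confirmation. This matches the relapse rule.
2. Use one date-based cut-off in SAP 6.3, SAP 10.1 and the Table 3 note: exclude values dated after the start date of the new HCV treatment. A discontinuation-visit sample taken on that date is then kept. A test based on the time of the first new dose is not workable, because Protocol 5.2.3 asks for medication dates and not times.

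The cost is a few words in the SAP and a small programming change. There are two drawbacks. An unconfirmed blip just before a switch would count as failure, as it already does for relapse. A same-day sample could also have been drawn after the first new dose, which dates alone cannot show. No change to the protocol's stopping criteria is needed or suggested.
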